# 12.2 Methods of statistical analyses

Statistical methods will be descriptive. For continuous data, descriptive statistics will be presented as number of patients (n), mean, standard deviation (SD), median, minimum and maximum. For categorical data, the frequency and percentage of patients in each category will be presented. Counts that are zero will be displayed as "0". Percentages will be based on non-missing data unless otherwise specified.

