### Study centre(s) and number of subjects planned

This study will be conducted in approximately 100 investigational centres in China. It is expected that approximately 2000 patients will be enrolled into study treatment.

Study period		Phase of development
Estimated date of first subject enrolled	Q2 2013	Phase IV
Estimated date of last subject completed	Q4 2015	

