# **1.3** Rationale for conducting this study

Post-hoc analyses in subgroups of Asian and Chinese patients are shown (Table 1).

Table 1

I uote I		incucy and biccu			
	ticagre	lor	clopido	grel	HR (95% CI)
	n	N with events (KM%)	n	N with events (KM%)	
Primary eff	ficacy end	point (composite of	f CV death	, MI, stroke,)	
Overall	9333	864 (9.8)	9291	1014 (11.7)	0.84 (0.77-0.92)
Asian	533	67 (13.0)	523	79 (16.2)	0.82 (0.59-1.14)
China	209	18 (8.7)	207	23 (11.3)	0.77 (0.42-1.43)
Primary sa	fety endpo	int (PLATO-defin	ed total ma	ajor bleed)	
Overall	9235	961 (11.6)	9186	929 (11.2)	1.04 (0.95-1.13)
Asian	526	53 (10.9)	515	48 (10.8)	1.07 (0.73-1.59)
China	207	14 (7.2)	203	8 (4.2)	1.72 (0.72-4.09)
Fatal/life-th	reatening	bleed			
Overall	9235	491 (5.8)	9186	480 (5.8)	1.03 (0.90-1.16)
Asian	526	33 (6.8)	515	29 (6.1)	1.10 (0.67-1.81)
China	207	11 (5.7)	203	6 (3.2)	1.81 (0.67-4.88)
Fatal bleed					
Overall	9235	20 (0.3%)	9291	23 (0.3%)	0.87 (0.48, 1.59)
Asian	526	2 (0.5%)	515	2 (0.4%)	0.97 (0.14, 6.87)
China	207	1 (0.5%)	203	0	

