# **11.2** Calculation or derivation of safety variable(s)

The safety assessment will describe total major bleeding events (including the subsets of fatal and fatal/ life threatening events), combined major and minor bleeding events and major/minor/minimal bleeding events. Bleeding events will be analyzed according to locally adjudicated PLATO bleeding definitions. AEs and other SAEs other than bleeding will also be evaluated. Summaries will be presented using descriptive statistics.

- Primary variables
  - PLATO-defined fatal/life-threatening bleedings during 1 year follow up in Chinese ACS patients treated with ticagrelor.

- PLATO-defined major bleedings during 1year follow up in Chinese ACS patients treated with ticagrelor.
- PLATO-defined major + minor bleedings during 1 year follow up in Chinese ACS patients treated with ticagrelor.
- PLATO-defined major + minor + minimal bleedings during 1 year follow up in Chinese ACS patients treated with ticagrelor.
- Serious adverse events other than bleeding during 1 year follow up in Chinese ACS patients treated with ticagrelor.
- Other variable

Major CV events during 1 year follow up in Chinese ACS patients treated with ticagrelor.

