# 12. STATISTICAL METHODS AND SAMPLE SIZE DETERMINATION BY ASTRAZENECA

# 12.1 Description of analysis sets

All subjects who received at least one dose of investigational product, and for whom any postdose data are available will be included in the safety population.

Patients will be censored at 7 days after their last dose of ticagrelor. Patients who withdraw consent to participate in the study will be included up to the date of their study termination. Primary analyses of all safety variables will use the safety analysis set.

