# **12.3** Determination of sample size

This is a regulatory commitment study to investigate the incidence of safety profile of ticagrelor including fatal/life-threatening bleeding among Chinese ACS patients within 1 year of follow up. If the fatal/life-threatening bleeding rate is 5.7% then 2000 patients would allow this to be estimated with a precision of  $\pm/-1\%$ , with a 95%CI.

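### Sections 12.1, 12.2 and 12.3 do not fit together: censoring after last dose, a plain percentage as the only stated summary, and a Kaplan-Meier planning rate with a 95% CI

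*Protocol*

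**What the plan says.** The primary variables (synopsis and Protocol section 11.2) are PLATO-defined bleedings, in four groupings, and non-bleeding SAEs, each over one year of follow-up. Section 12.3 likewise describes the aim as incidence within one year.

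Section 12.1 limits the time that counts: "Patients will be censored at 7 days after their last dose of ticagrelor". It adds: "Patients who withdraw consent to participate in the study will be included up to the date of their study termination". Section 5.8.3 asks patients who stop drug to stay in follow-up to month 12, so the shortened time at risk comes mainly from the analysis rule, not from lost data.

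Section 12.2, repeated in the synopsis, describes the methods as descriptive. For event data it offers one summary: "For categorical data, the frequency and percentage of patients in each category will be presented". The denominator rule is: "Percentages will be based on non-missing data unless otherwise specified". Section 11.2 says of the safety variables only: "Summaries will be presented using descriptive statistics". Kaplan-Meier appears in the abbreviation list and in Table 1, never as a planned method.

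Section 12.3 sizes the trial on precision: "If the fatal/life-threatening bleeding rate is 5.7% then 2000 patients would allow this to be estimated with a precision of" plus or minus 1%, with a 95% CI. It does not name the source of 5.7%, but the figure equals the China ticagrelor entry for fatal/life-threatening bleeding in Table 1 (11 events in 207 patients), in a column whose heading begins "N with events (KM".

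**The concern.** Censoring belongs to time-to-event estimation, and a plain percentage has no place for a censored patient. Someone who stops drug at month 2 without a bleed, and is censored a week later, enters the percentage exactly like someone who took drug for twelve months without a bleed. The result is a proportion with an on-treatment bleed over unequal exposure times. It equals one-year incidence only if nobody is censored early.

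This matters because describing these rates is the primary objective of a study required by the regulator, and a single arm offers no comparison in which the shortfall could cancel. The sections also use three different quantities: an on-treatment observation window (12.1), a plain percentage (12.2) and a planning rate on the Kaplan-Meier scale with a 95% CI (12.3).

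**Working it through.** **Inputs from the protocol.** Planning rate 5.7%, n = 2000, 95% CI, stated precision ±1% (section 12.3); counts and Kaplan-Meier percentages (Table 1); censoring rule (section 12.1). **Not in the protocol:** the share of patients who stop drug within the year. It is assumed below at 10% to 40%.

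**1. The plan's own figure.** Half-width = 1.96 × √(p(1−p)/n) = 1.96 × √(0.057 × 0.943 / 2000) = 1.016 points, which rounds to the stated ±1%. Other intervals agree: Wilson 4.77% to 6.80%; exact, with 114/2000, 4.72% to 6.81%. The formula treats 5.7% as a binomial proportion with every patient observed for the full year.

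**2. The scale of the planning rate.** Plain percentages from the ticagrelor rows of Table 1, against the Kaplan-Meier values printed there:

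| Row | Plain | Kaplan-Meier | Gap (points) |
|---|---|---|---|
| China, fatal/life-threatening | 11/207 = 5.31% | 5.7% | 0.39 |
| China, total major | 14/207 = 6.76% | 7.2% | 0.44 |
| Overall, fatal/life-threatening | 491/9235 = 5.32% | 5.8% | 0.48 |
| Overall, total major | 961/9235 = 10.41% | 11.6% | 1.19 |

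So the two scales differ visibly in the protocol's own data. Planning on 5.31% would give a half-width of 0.98 points, which also rounds to 1%, so the sample size does not depend on this.

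**3. Size of the shortfall here (illustration).** Assume a true one-year risk of 5.7%, a share d of patients stopping drug at a constant rate over the year, stopping unrelated to bleeding, and, for simplicity, censoring at the stop itself; the 7 extra days would shrink the shortfall slightly. Put λ_b = −ln(1 − 0.057) and λ_c = −ln(1 − d). With a constant bleeding hazard,

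expected plain percentage = λ_b/(λ_b + λ_c) × [1 − exp(−(λ_b + λ_c))].

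For d = 20%: λ_b = 0.0587, λ_c = 0.2231, sum 0.2818; 0.0587/0.2818 × (1 − 0.7544) = 5.11%. The early-bleeding case puts half of the cumulative bleeding hazard in the first 30 days and is integrated numerically.

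**4. Precision of a Kaplan-Meier one-year estimate.** By Greenwood's formula in the constant-hazard case, with S = 0.943 at one year,

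variance = S² × (λ_b/n) × [exp(λ_b + λ_c) − 1]/(λ_b + λ_c).

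For d = 20% this gives a half-width of 1.08 points.

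| Assumed stopping | Plain %, constant hazard | Plain %, early bleeding | Shortfall from 5.7% (points) | KM half-width, constant | KM half-width, early |
|---|---|---|---|---|---|
| 10% | 5.41 | 5.53 | 0.17 to 0.29 | 1.04 | 1.03 |
| 20% | 5.11 | 5.36 | 0.34 to 0.59 | 1.08 | 1.05 |
| 30% | 4.80 | 5.18 | 0.52 to 0.90 | 1.12 | 1.08 |
| 40% | 4.47 | 4.98 | 0.72 to 1.23 | 1.16 | 1.10 |

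**The case against.** The strongest reply is that section 12.2 gives a general rule for categorical data and never says outright that bleeding will be shown as a plain percentage. A Kaplan-Meier curve is also descriptive, the word censored suggests that one may be intended, and the SAP, which is not at hand, commonly fixes the estimator. This stands as a limit on the point: silence on technical detail is not the fault. But frequency and percentage is the only summary stated for these variables, in the body and in the synopsis, and it does not fit the stated censoring rule. An SAP faithful to section 12.2 would carry the mismatch forward.

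A second reply is that a plain percentage within last dose plus 7 days is a valid on-treatment proportion. That is correct. It is too low only when read as one-year incidence, which is how the objectives and variables describe it.

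Four stronger readings are tempting, and the documents do not support them:

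- A reader might infer that no confidence interval is planned. Section 12.3 does tie the estimate to a 95% CI; section 12.2 merely fails to carry it through.
- A reader might infer from the non-missing rule that early-censored patients leave the denominator and push the rate up. An event-free patient who stops early has an observed on-treatment status, and nothing says that such patients are missing.
- A reader might carry the Table 1 gaps over to this trial as its expected bias. The protocol gives neither the earlier trial's follow-up distribution nor its censoring rule, so they show only that the two scales differ.
- A reader might compute precision as if early stoppers contributed nothing: ±1.14 points with 1600 patients for 20% stopping. They contribute until censored, and the Kaplan-Meier half-width is then 1.05 to 1.08.

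**Conclusion.** The point holds as a mismatch among three sections. Followed as written, the plan would report a figure below one-year bleeding incidence by an amount that depends on early stopping: about 0.2 to 1.2 points below a true 5.7% for an assumed 10% to 40% stopping, with stopping taken as unrelated to bleeding. At the upper end that is as large as the stated precision. The planning rate is on the Kaplan-Meier scale and the stated summary is not, but this leaves the sample size intact, and ±1% is correctly computed for complete follow-up. Severity is moderate; this is a cheap improvement rather than a flaw that undermines the trial.

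**What to change.** **Section 12.2.** State that each primary bleeding variable is estimated as 12-month cumulative incidence from first dose under the section 12.1 censoring rule, with a 95% CI. Kaplan-Meier suffices; a competing-risk version (death as the competing event) can be left to the SAP. Show the count and plain percentage beside it, labelled as an on-treatment proportion of the whole safety set. State that the non-missing denominator does not apply to event variables.

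**Section 12.3.** Note that 5.7% is a Kaplan-Meier figure and that ±1% (1.02) assumes complete follow-up, becoming roughly ±1.03 to ±1.16 under an assumed 10% to 40% stopping.

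**Cost.** A few lines and no new data. The reported rate will be slightly higher and the interval slightly wider. The estimate still assumes that stopping drug is unrelated to later bleeding risk. Because sections 5.8 and 5.8.2 provide for stopping after adverse events and significant bleeds, the text should acknowledge that assumption.

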# **12.3** Determination of sample size

This is a regulatory commitment study to investigate the incidence of safety profile of ticagrelor including fatal/life-threatening bleeding among Chinese ACS patients within 1 year of follow up. If the fatal/life-threatening bleeding rate is 5.7% then 2000 patients would allow this to be estimated with a precision of  $\pm/-1\%$ , with a 95%CI.

# **12.4** Data monitoring committee (Not applicable)

# 13. IMPORTANT MEDICAL PROCEDURES TO BE FOLLOWED BY THE INVESTIGATOR

# **13.1** Medical emergencies and AstraZeneca contacts

The Principal Investigator is responsible for ensuring that procedures and expertise are available to handle medical emergencies during the study. A medical emergency usually constitutes an SAE and is to be reported as such, see Section 6.4.4

In the case of a medical emergency the investigator may contact the Study Delivery Team Leader. If the Study Delivery Team Leader is not available, contact the Study Delivery Team Physician at the AstraZeneca Research and Development.

Name	Role in the study	Address & telephone number
	Study Delivery Team Leader responsible for the protocol at central R&D site	
	SDT Physician responsible for the protocol at central R&D site	
	24-hour emergency cover at central R&D site.	

# 13.2 Overdose

An overdose of ticagrelor is defined as intake of 4 or more ticagrelor tablets (360 mg)/day.

In the event of an overdose of ticagrelor, ascertain the time and extent of the overdose regardless of severity. Determine the causative circumstance and whether haemorrhagic or toxic complications have occurred or are likely to do so. Depending on these facts, the appropriate health care provider should decide if the patient should be hospitalised for observation or not.

Bleeding is one of the most likely pharmacological effects of excessive ticagrelor dosing, and appropriate supportive measures such as volume replacement, local haemostatic measures, and decompression or drainage may be required depending on the extent of bleeding or volume of blood lost. Patients with overdose-related bleeding should be cautioned to avoid unnecessary activity, mechanical tissue stress, and minor trauma for at least 24 hours after the bleeding has stopped. For other symptoms that can be expected after an overdose of ticagrelor and additional information see the IB.

- An overdose with associated AEs is recorded as the AE diagnosis/symptoms on the relevant AE modules in the CRF and on the Overdose CRF module.
- An overdose without associated symptoms is only reported on the Overdose CRF module.

If an overdose on an AstraZeneca study drug occurs in the course of the study, then investigators or other site personnel inform appropriate AstraZeneca representatives immediately, or **no later than 24 hours** of when he or she becomes aware of it.

The designated AstraZeneca representative works with the investigator to ensure that all relevant information is provided to the AstraZeneca Patient Safety data entry site.

For overdoses associated with SAE, standard reporting timelines apply, see Section 6.4.4. For other overdoses, reporting should be done within 30 days.

# 13.3 Pregnancy

All outcomes of pregnancy should be reported to AstraZeneca.

# **13.3.1** Maternal exposure

If a subject becomes pregnant during the course of the study investigational product should be discontinued immediately.

Pregnancy itself is not regarded as an adverse event unless there is a suspicion that the investigational product under study may have interfered with the effectiveness of a contraceptive medication. Congenital abnormalities/birth defects and spontaneous miscarriages should be reported and handled as SAEs. Elective abortions without complications should not be handled as AEs. The outcome of all pregnancies (spontaneous miscarriage, elective termination, ectopic pregnancy, normal birth or congenital abnormality) should be followed up and documented even if the subject was discontinued from the study.

If any pregnancy occurs in the course of the study, then investigators or other site personnel inform appropriate AstraZeneca representatives immediately, or **no later than 24 hours** of when he or she becomes aware of it.

The designated AstraZeneca representative works with the investigator to ensure that all relevant information is provided to the AstraZeneca Patient Safety data entry site within 1 or 5 days for SAEs, see Section 6.4.4 and within 30 days for all other pregnancies.

The same timelines apply when outcome information is available.

# Appendix B Additional Safety Information

# FURTHER GUIDANCE ON THE DEFINITION OF A SERIOUS ADVERSE EVENT (SAE)

### Life threatening

'Life-threatening' means that the subject was at immediate risk of death from the AE as it occurred or it is suspected that use or continued use of the product would result in the subject's death. 'Life-threatening' does not mean that had an AE occurred in a more severe form it might have caused death (eg, hepatitis that resolved without hepatic failure).

### Hospitalisation

Outpatient treatment in an emergency room is not in itself a serious AE, although the reasons for it may be (eg, bronchospasm, laryngeal oedema). Hospital admissions and/or surgical operations planned before or during a study are not considered AEs if the illness or disease existed before the subject was enrolled in the study, provided that it did not deteriorate in an unexpected way during the study.

### Important medical event or medical intervention

Medical and scientific judgement should be exercised in deciding whether a case is serious in situations where important medical events may not be immediately life threatening or result in death, hospitalisation, disability or incapacity but may jeopardize the subject or may require medical intervention to prevent one or more outcomes listed in the definition of serious. These should usually be considered as serious.

Simply stopping the suspect drug does not mean that it is an important medical event; medical judgement must be used.

Examples of such events are:

- Angioedema not severe enough to require intubation but requiring iv hydrocortisone treatment
- Hepatotoxicity caused by paracetamol (acetaminophen) overdose requiring treatment with N-acetylcysteine
- Intensive treatment in an emergency room or at home for allergic bronchospasm
- Blood dyscrasias (eg, neutropenia or anaemia requiring blood transfusion, etc) or convulsions that do not result in hospitalisation
- Development of drug dependency or drug abuse.

# A GUIDE TO INTERPRETING THE CAUSALITY QUESTION

The following factors should be considered when deciding if there is a "reasonable possibility" that an AE may have been caused by the drug.

- Time Course. Exposure to suspect drug. Has the subject actually received the suspect drug? Did the AE occur in a reasonable temporal relationship to the administration of the suspect drug?
- Consistency with known drug profile. Was the AE consistent with the previous knowledge of the suspect drug (pharmacology and toxicology) or drugs of the same pharmacological class? OR could the AE be anticipated from its pharmacological properties?
- Dechallenge experience. Did the AE resolve or improve on stopping or reducing the dose of the suspect drug?
- No alternative cause. The AE cannot be reasonably explained by another aetiology such as the underlying disease, other drugs, other host or environmental factors.
- Rechallenge experience. Did the AE reoccur if the suspected drug was reintroduced after having been stopped? AstraZeneca would not normally recommend or support a rechallenge.
- Laboratory tests. A specific laboratory investigation (if performed) has confirmed the relationship?

A "reasonable possibility" could be considered to exist for an AE where one or more of these factors exist.

In contrast, there would not be a "reasonable possibility" of causality if none of the above criteria apply or where there is evidence of exposure and a reasonable time course but any dechallenge (if performed) is negative or ambiguous or there is another more likely cause of the AE.

In difficult cases, other factors could be considered such as:

- Is this a recognised feature of overdose of the drug?
- Is there a known mechanism?

Ambiguous cases should be considered as being a "reasonable possibility" of a causal relationship unless further evidence becomes available to refute this. Causal relationship in cases where the disease under study has deteriorated due to lack of effect should be classified as no reasonable possibility.

Clinical Study Protocol Appendix C				
Drug Substance	Ticagrelor			
Study Code	D5130C00087			
Edition Number	1.0			
Date	8 May 2013			

# Appendix C International Airline Transportation Association (IATA) 6.2 Guidance Document

# LABELLING AND SHIPMENT OF BIOHAZARD SAMPLES

International Airline Transportation Association (IATA) classifies biohazardous agents into 3 categories

(http://www.iata.org/whatwedo/cargo/dangerous\_goods/infectious\_substances.htm). For transport purposes the classification of infectious substances according to risk groups was removed from the Dangerous Goods Regulations (DGR) in the 46th edition (2005). Infectious substances are now classified either as Category A, Category B or Exempt. There is no direct relationship between Risk Groups and categories A and B.

**Category A Infectious Substances** are infectious substances in a form that, when exposure to it occurs, is capable of causing permanent disability, life-threatening or fatal disease in otherwise healthy humans or animals. Category A pathogens are eg, Ebola, Lassa fever virus:

• are to be packed and shipped in accordance with IATA Instruction 602.

**Category B Infectious Substances** are infectious Substances that do not meet the criteria for inclusion in Category A. Category B pathogens are eg, Hepatitis A, B, C, D, and E viruses, Human immunodeficiency virus (HIV) types 1 and 2. They are assigned the following UN number and proper shipping name:

- UN 3373 Biological Substance, Category B
- are to be packed in accordance with UN3373 and IATA 650

**Exempt** - all other materials with minimal risk of containing pathogens

- Clinical trial samples will fall into Category B or exempt under IATA regulations
- Clinical trial samples will routinely be packed and transported at ambient temperature in IATA 650 compliant packaging (http://www.iata.org/whatwedo/cargo/dangerous\_goods/infectious\_substances. htm)
- Biological samples transported in dry ice require additional dangerous goods specification for the dry-ice content
- IATA compliant courier and packaging materials should be used for packing and transportation and packing should be done by an IATA certified person, as applicable

- •
- Samples routinely transported by road or rail are subject to local regulations which require that they are also packed and transported in a safe and appropriate way to contain any risk of infection or contamination by using approved couriers and packaging / containment materials at all times. The IATA 650 biological sample containment standards are encouraged wherever possible when road or rail transport is used.

